5. INTERVENTIONAL TREATMENT OF SUBJECTS

5.1 Randomization to the 'restricted PEEP'-arm or the 'liberal PEEP'-arm

Patients are randomly assigned in a 1:1 ratio to the 'restricted PEEP'-arm or to the 'liberal PEEP'-arm of this trial.

5.2 The 'restricted PEEP'-arm

Directly after start of invasive ventilation the PEEP level is set at 5 cm H₂O with an inspired oxygen fraction (FiO₂) between 0.21 and 0.6. The goal is to ventilate with the lowest possible PEEP level resulting in an acceptable level of oxygenation. For this, the operator, usually the attending ICU nurse, will reduce the level of PEEP in steps of 1 cm H₂O to a minimum level of 0 cm H₂O. Every 15 minutes the PEEP level is reduced with 1 cm H₂O, as long as the pulse oximetry reading shows a SpO₂ > 92% or the arterial blood gas shows a PaO₂ > 8 kPa, as illustrated in the flowchart (see **Figure 1**). Thereafter, ventilation continues with the lowest PEEP level at which the SpO₂ > 92% or PaO₂ > 8 kPa, using a FiO₂ of between 0.21 and 0.6. In case the SpO₂ drops below 92% or the PaO₂ drops below 8 kPa, brief periods of 5 minutes may be tolerated, first FiO₂ is increased up to maximum 0.6 before the level of PEEP is increased in steps of 1 cm H₂O until 5 cm H₂O. As soon as the patient stabilizes, again the level of PEEP is reduced in steps of 1 cm H₂O to a minimum level of 0 cm H₂O.

So-called 'down-titrations' of the PEEP level are allowed as often as wanted, but with a minimum of three 'down-titrations' per ICU nurse shift (i.e., every eight hours). This number is chosen to push nurses towards using the lowest possible PEEP level. We deliberately chose not to state a maximum for these 'down-titrations', as adjustments in ventilator settings, like FiO₂ and driving pressure, in the Dutch ICU setting are very frequent, occurring many more times than three times per shift – this is a safe process, and we assume it is the same for the PEEP level adjustments.

Patients are weaned from the ventilator (see: weaning) and tracheally extubated using the lowest PEEP level. In other words, the lowest PEEP level is used throughout the complete period of invasive ventilation. However, during pulmonary toileting and tracheal suctioning, bronchoscopic procedures, intra- or inter-ICU transport or any maneuver during which 'pre-oxygenation' with high FiO₂ is deemed beneficial, ICU nurses are allowed to increase the FiO₂ > 0.6, and preferably not the level of PEEP.

Pulmonary rescue: in case of severe hypoxemia, defined as a drop in SpO₂ below 88% or a drop in PaO₂ below 7.3 kPa, common causes such as a mucus plug

requiring pulmonary toilet should be considered and treated, the FiO_2 level is increased up to 1.0 and the PEEP level is set back at 5 cm H_2O or more, both to a level left to the discretion of the attending physician. After solving the cause for the drop in SpO_2 or PaO_2 , the PEEP level is again ‘down–titrated’, following the same steps as described above. Development of atelectasis, or increases in the amount of atelectasis is not necessarily a reason for using a higher PEEP level, unless the SpO_2 drops below 92% or the PaO_2 drops below 8 kPa, and does not respond to increases in FiO_2 to maximal 0.6. If a patient develops ARDS, according to the Berlin definition for ARDS,^{36,37} the level of PEEP should always be increased to 10 cm H_2O , or more.

Hemodynamic rescue: in case a patient becomes hemodynamic unstable, meaning that more inotropes and/or vasoactive agents are needed, hemodynamic compromise due to increases in atelectasis could be considered. Then, for a short period of time (e.g., for 1 to 2 hours) the PEEP level can be set at 5 cm H_2O . After solving the hemodynamic problem, the PEEP level is again ‘down–titrated’.

5.3 The ‘liberal PEEP’–arm

Directly after start of invasive ventilation the PEEP level is set at 8 cm H_2O with a FiO_2 between 0.21 and 0.6. The goal is to ventilate the patient mainly at this level of PEEP till tracheal extubation. For this, the operator will increase the level of PEEP, if a level of < 8 cm H_2O was used, to 8 cm H_2O in one single step (see **Figure 1**). Thereafter, ventilation continues with the PEEP level at 8 cm H_2O using a FiO_2 of between 0.21 and 0.6. In case the SpO_2 drops below 92% or the PaO_2 drops below 8 kPa, first FiO_2 is increased to maximum 0.6 before the level of PEEP is further increased.

Patients are weaned of the ventilator (see: weaning) and tracheally extubated using a PEEP level of 8 cm H_2O . However, during pulmonary toileting and tracheal suctioning, bronchoscopic procedures, intra– or inter–ICU transport or any maneuver during which ‘pre–oxygenation’ with high FiO_2 is deemed beneficial, ICU nurses are allowed to increase the $\text{FiO}_2 > 0.6$, and preferably not the level of PEEP. If preferred, the level of PEEP can be set at 5 cm H_2O for one to two hours directly before tracheal extubation, left to the discretion of the attending physician.

[figure not shown]
Pulmonary rescue: in case of severe hypoxemia, defined as a drop in SpO_2 below 88% or a drop in PaO_2 below 7.3 kPa, common causes such as a mucus plug requiring pulmonary toilet can be considered and treated, FiO_2 level is increased up to 1.0 to a level left to the discretion of the attending physician, if necessary the PEEP

level can be increased. After solving the cause for the drop in SpO₂ or the drop in PaO₂, FiO₂ and the level of PEEP is set back.

Hemodynamic rescue: in case a patient becomes hemodynamic unstable, meaning that more inotropes and/or vasoactive agents are needed, hemodynamic compromise due to increases in overdistension could be considered. Then, for a short period of time (e.g., for 1 to 2 hours) the PEEP level can be set at 5 cm H₂O. After solving the hemodynamic problem, the level of PEEP is again set back to 8 cm H₂O.

The goal is to ventilate patients in this arm with a PEEP level of 8 cm H₂O and only to adjust the PEEP level when deemed necessary. This reflects current ventilation practice in the Dutch setting, where the PEEP level is further increased to improve oxygenation, but decreased in case of hemodynamic compromise (see **Figure 1**).

Figure 1. Flowchart ventilator settings in the 'restricted PEEP'-arm and in the 'liberal PEEP'-arm

* = 94-96%, ** = 88-93%, higher oxygen targets are allowed for patients who develop:

- 1) ongoing cardiac ischemia due to cardiac infarction and failed revascularisation
- 2) delayed cerebral ischemia after subarachnoid hemorrhage
- 3) increased and uncontrollable intracranial pressure (> 18 mmHg)
- 4) necrotizing fascitis
- 5) severe untreatable anemia, such as in case of Jehovah's Witnesses

[#], short periods of PEEP at 5 cm H₂O are allowed to evaluate whether the patient can be extubated

Abbreviations: PEEP, positive end-expiratory pressure; MV, mechanical ventilation; PBW, predicted body weight; ARDS, acute respiratory distress syndrome.

In APPENDIX III a few patient examples are shown to clarify and explain the proposed ventilation strategy in the 'restricted PEEP'-arm.

6. STANDARD TREATMENT OF SUBJECTS

6.1 Standard ventilatory management

The RELAX trial allows the following ventilatory modes: volume-controlled or pressure-controlled ventilation, and pressure support ventilation. Automated modes, in particular those that automatically change the PEEP level and FiO_2 , are never allowed.

With volume-controlled and pressure-controlled ventilation the inspiration-to-expiration ratio is set at 1:2. With volume-controlled ventilation the inspiration time and pause are set at 25% and 10%, respectively. With pressure support ventilation, the highest possible pressure rise is chosen and cycling off is set at 25%.

Tidal volume size is between 6–8 ml/kg predicted body weight (PBW), which is calculated according to the following formula³⁸ $50 + 0.91 \times (\text{centimeters of height} - 152.4)$ for males and $45.5 + 0.91 \times (\text{centimeters of height} - 152.4)$ for females. The respiratory rate is adjusted to obtain a normal arterial blood pH (7.35 to 7.45). In case of metabolic acidosis or alkalosis, a lower or higher than normal PaCO_2 can be accepted, which is left to the discretion of the attending physician. Recruitment maneuvers are allowed when deemed necessary, but the decision to perform a recruitment maneuver is also left to the discretion of the attending physician.

6.2 Oxygenation targets

The oxygenation target ranges for SpO_2 and PaO_2 are 92% to 96%, and 8 kPa to 11.5 kPa, respectively.³⁹⁻⁴³ Oxygenation will be maintained in the target ranges primarily by adjusting the FiO_2 , which is typically set between 0.21 and 0.6. The oxygenation target is primarily assessed by peripheral saturation (SpO_2) as measured by pulse oximetry and only in case of unreliable reading the oxygenation will be assessed by the arterial blood oxygen pressure (PaO_2).

For patients in whom the risk of potentially dangerous hypoxemia could be become unacceptable during the trial (e.g., in patients who develop: ongoing cardiac ischemia due to cardiac infarction and failed revascularization, delayed cerebral ischemia after subarachnoid hemorrhage, increased and uncontrollable intracranial pressure (of ≥ 18 mmHg), necrotizing fasciitis or severe untreatable anemia such as with Jehovah's Witnesses), the oxygenation target ranges can be increased to SpO_2 and PaO_2 of 94% to 96%, and 9 kPa to 11.5 kPa, respectively.

6.3 Ventilator settings when a patient develops ARDS

In case a patient develops ARDS, ventilation should be continued according to existing guidelines for patients with ARDS. This at least consists of low tidal volumes (6 ml/kg PBW or lower), and higher PEEP levels (10 cm H₂O or higher). Also, a low driving pressure could be considered.

6.4 Ventilator settings when a patient requires ECMO

In the unlikely event that a patient receives ECMO, the ventilator is set according to the local protocol for ventilation under ECMO. This means that PEEP is *no longer* titrated according to the study protocol.

6.5 Weaning

In all patients who receive assist ventilation, three times a day it should be tested whether the patient accepts assist ventilation; this should also be tried when the patient shows respiratory muscle activity during assist ventilation.

The attending physician decides when to tracheally extubate a patient, based on general extubation criteria (i.e. responsive and cooperative, adequate cough reflex, adequate oxygenation with FiO₂ ≤ 0.4, hemodynamically stable, no uncontrolled arrhythmia and a rectal temperature > 36 Celsius and after successfully passing a spontaneous breathing trial (SBT) with a T-piece *or* ventilation with minimal support (pressure support level < 10 cm H₂O) and FiO₂ ≤ 0.4. In case SBTs are used, an SBT is judged as successful when the following criteria are met for at least 30 minutes, the attending physician takes the final decision for extubation:

- Respiratory rate < 35/min
- Peripheral oxygen saturation > 90%
- Increase < 20% of Heart rate and blood pressure
- No signs of anxiety and diaphoresis

In case a patient needs to be re-intubated and ventilated, the PEEP level is set as described above.

6.6 Tracheostomy

Early tracheostomy has no advantage over late tracheotomy.⁴⁴ Therefore, tracheostomy is only to be performed on strict indications and preferably not earlier than 10 days after intubation. Strict indications for tracheostomy:

- Expected duration of ventilation > 14 days

- Glasgow Coma Score < 7 and/or inadequate swallow or cough reflex with retention of sputum
- Severe ICU-acquired weakness
- Repeated respiratory failure after extubation
- Pre-existent diminished pulmonary reserves
- Failure to intubate
- Prolonged or unsuccessful weaning

Weaning with a tracheostomy follows recommendations as described under 'weaning', a suggested scheme for unassisted ventilation with a tracheostomy is described in APPENDIX II.

6.7 Sedation protocol

Sedation follows the local guidelines for sedation in each participating unit. In general, these guidelines favor the use of analgo-sedation over hypno-sedation, use of bolus over continuous infusion of sedating agents, and the use of sedation scores.

Nurses determine the level of sedation at least 3 times per day. The adequacy of sedation in each patient is evaluated using a Richmond Agitation Sedation Scale (RASS).^{45,46} A RASS score of -2 to 0 is seen as adequate sedation. The goals of sedation are to reduce agitation, stress and fear; to reduce oxygen consumption (heart rate, blood pressure and minute volume are measured continuously); and to reduce physical resistance to— and fear of daily care and medical examination. Patient comfort is the primary goal.

Level of pain is determined using scales such as Numeric Rating Scale (NRS), Visual Analogue Scale (VAS), Critical Care Pain Observation Tool (CCPOT) or Behavioral Pain Scale (BPS).

6.8 Non-ventilatory management

6.8.1 Selective oropharyngeal- or digestive tract decontamination

To prevent nosocomial infections, selective oropharyngeal decontamination (SOD) or selective decontamination of the digestive tract (SDD) is performed in all patients who are expected to need ventilation for longer than 48 hours, and/or are expected to stay in ICU for longer than 72 hours.⁴⁷

6.8.2 Thrombosis prophylaxis

Thrombosis prophylaxis is indicated for all patients who are not treated with anticoagulants, e.g. for therapeutic reasons or systemic prophylaxis because of an

implanted device or extracorporeal circulation like for renal replacement therapy. Thrombosis prophylaxis will be given according to local guidelines.

6.8.3 Fluid regimens

A fluid balance targeted at normovolemia and a diuresis of ≥ 0.5 ml/kg/hour should be maintained. Crystalloid infusions are preferred over colloid infusions.

6.8.4 Nutrition

A hypo-caloric, protein-rich diet (1.2–1.7 gr/kg bodyweight /24 hours) is started as soon as possible after ICU admission. Enteral nutrition with a feeding gastric tube is preferred over intravenous feeding. If stomach retention occurs, a duodenal tube can be used if administration of prokinetic drugs is not sufficient, according to local guidelines. When optimal protein intake cannot be reached within 4 days, additional parenteral nutrition can be started.

7. METHODS

7.1 Study parameters/endpoints

7.1.1 Main study parameter

The primary endpoint is the number of ventilator-free days and alive at day 28, defined as the number of days from day 1 to day 28; the patient is alive and breathes without assistance of the mechanical ventilator, if the period of unassisted breathing lasted at least 24 consecutive hours.

7.1.2 Secondary study parameters

Secondary study parameters include:

- ICU length of stay (LOS)
- Hospital LOS
- ICU mortality
- Hospital mortality
- 90-day mortality
- Incidence of development ARDS (APPENDIX I)
- Incidence of severe hypoxemia (APPENDIX I)
- Incidence of severe atelectasis, if a chest radiograph is obtained (APPENDIX I)
- Rescue therapies for severe hypoxemia or severe atelectasis
 - Recruitment maneuver (APPENDIX I)
 - Prone positioning
 - Bronchoscopy for opening atelectasis
- Incidence of pneumothorax, if a chest radiograph is obtained or other kind of imaging suitable for diagnosing pneumothorax is obtained (APPENDIX I)
- Incidence of pneumonia (APPENDIX I)
- The level of PEEP in the 'restricted PEEP'-arm and the 'liberal PEEP'-arm
- Days with use of hemodynamic support, defined as the number of ICU days with any use of vasopressors/inotropes for > 1 hour on a day
- Days with use of sedation, defined as the number of ICU days with any use of sedatives for > 1 hour on a day
- Therapeutic intervention scoring system (TISS)/ Nursing Activities Score (NAS)

7.1.3 Other study parameters

Health care related costs will be estimated from the health systems perspective over the time horizon of this trial. Costs include costs of ventilation, costs of stay in ICU,

costs of stay in hospital, costs of use of inotropes and vasopressors, costs of use of sedatives, costs of use of tracheostomies, costs of ventilator-associated pneumonia. Costs will be determined for both PEEP arms during the 28 days follow up period after initial ICU admission. These are used to calculate incremental cost per mechanical ventilation-day avoided.

Lung ultrasound (LUS): within 12 hours after enrolment in the RELAX study, after 24-48 hours after enrolment and within 24 hours after extubation, a LUS will be performed to monitor changes in lung aeration. This is only done in patients admitted to the AMC (see appendix IV: RELAXLUS).

Cardiac ultrasound (ECHO): 24-48 hours after enrolment in the RELAX study, a transthoracic echocardiography (TTE) will be performed to assess the cardiac function. This is only done in a total of 68 patients admitted to the AMC (see appendix V: RELAXECHO).

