2.1.2. Secondary objectives

Secondary objectives are to compare the effects of '*restricted PEEP*' vs. '*liberal PEEP*' on ICU- and hospital length of stay (LOS), ICU- and hospital, and 90-day mortality, the incidence of severe hypoxemia, severe atelectasis, and the need for rescue therapies including recruitment maneuvers, bronchoscopy and prone position, pneumonia, pneumothorax, the incidence and development of ARDS, days with use of hemodynamic support and with use of sedation, therapeutic intervention scoring system (TISS)/ Nursing Activities Score (NAS) and related healthcare costs.

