2.2 Hypothesis

2.2.1 Primary hypothesis

We hypothesize that ventilation with the lowest possible PEEP level results in a similar number of ventilator-free days at day 28 as ventilation with the PEEP level currently practiced in ICU patients without ARDS.

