2.2.2. Secondary hypotheses

The secondary hypotheses are that ventilation with the lowest possible PEEP level is equal to ventilation with the PEEP level currently practiced in ICU patients without ARDS, with regard to the other endpoints mentioned above.

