9.4 Cost-effectiveness analysis

Alongside the proposed RCT a prospective economic study will be performed. The economic evaluation primarily focuses on the possible gained benefits of ventilation with the lowest possible PEEP versus ventilation with the PEEP level currently practiced and the associated healthcare costs within 28 days (the primary outcome of the RCT).

Incremental Cost Effectiveness Ratios (ICER) will be calculated by extra costs per TISS/NAS point, a valuable score reflecting workload and resource utilization in daily ICU practice.^{49,50} Cost calculations will be based on actual performance and resource use in routine ICU care during the study follow-up period.

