9.4.4. Statistical analysis of Cost-effectiveness

As most volumes of resource use follow a skewed distribution, differences between the two ventilation strategies will be statistically evaluated with bias-corrected bootstrap analysis.⁵² Incremental cost-effectiveness ratio will be calculated with the registered TISS/NAS-score as performance and effect parameter. The economic analysis will be expanded with a scenario-analysis to extrapolate the consequence of implementation and actual performance of the ventilation strategy with 'restricted PEEP' in the target population. The validity of the developed scenarios will be explored in a sensitivity analysis changing cost estimates and probabilities.

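### The stated cost-effectiveness result is a ratio whose denominator the trial itself expects to be about zero, and the protocol names two different denominators for it

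*Protocol*

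**What the plan says.** Section 7.1.3 determines costs in both arms over 28 days and states their use: "These are used to calculate incremental cost per mechanical ventilation-day avoided". Section 9.4 says that ICERs "will be calculated by extra costs per TISS/NAS point", and section 9.4.4 repeats that choice: "Incremental cost-effectiveness ratio will be calculated with the registered TISS/NAS-score as performance and effect parameter". So the protocol fixes a ratio of cost difference to effect difference as its cost-effectiveness result, with ventilation-days in one place and TISS/NAS points in the other two.

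On the expected effect, the primary hypothesis in 2.2.1 is that restricted PEEP "results in a similar number of ventilator-free days at day 28" as current practice. The secondary hypothesis in 2.2.2 is that it "is equal to ventilation with the PEEP level currently practiced", "with regard to the other endpoints mentioned above". Section 2.1.2 lists those endpoints and ends with "Nursing Activities Score (NAS) and related healthcare costs".

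Other economic outputs are planned that do not use the ratio: cost categories and overall costs compared with 95% CIs (9.4.1), a bias-corrected bootstrap of differences in resource use (9.4.4), and a budget impact analysis (9.5).

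**The concern.** An ICER is a cost difference divided by an effect difference. It is informative when the effect difference is clearly away from zero. In a non-inferiority trial that expects no difference, the estimated denominator scatters around zero. The ratio then takes large values of either sign, driven by sampling error in the denominator. A negative ratio is also ambiguous: it arises when the restricted arm is cheaper and better, and equally when it is dearer and worse.

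What is at stake is the one figure that the protocol presents as its cost-effectiveness result. In the scenario the trial is built to demonstrate, that figure would be hard or impossible to interpret. The two denominators add to this: an analyst following 7.1.3 and one following 9.4.4 would report different quantities in different units.

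**Working it through.** **1. What effect does the design assume?** Inputs from section 4.4: margin 10%, coefficient of variation (CV) 0.70, one-sided alpha 0.05, power 80%, 445 per arm.
- Log-scale SD = sqrt(ln(1 + 0.70²)) = 0.6315.
- Log-scale margin = −ln(0.9) = 0.1054.
- n per arm = 2 × [0.6315 × (1.645 + 0.842) / 0.1054]² ≈ 444.2, so 445. Exact power at 445 is 80.0%.

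The stated figure reproduces with a true difference of 0. Other readings do not fit: a margin of ln(1.1) gives 543, the raw scale gives 606, and one-sided 0.025 gives 564. So the sample size as well as the hypothesis takes the effect on ventilator-free days to be zero.

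**2. Where does that put each denominator?**
- TISS/NAS points: zero follows directly from 2.1.2 with 2.2.2. Costs are in the same list, so this ratio is expected to be 0/0.
- Ventilation-days avoided: zero is inferred from 2.2.1. Ventilator-free days also count deaths, so the two measures are close but not identical.

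**3. Precision of the ventilation-day denominator.** Mean 5 days (4.4) and 445 per arm (4.4). The protocol gives no CV for ventilation days, so 0.7 to 1.5 is an assumption. SE = 5 × CV × sqrt(2/445). Chances use a normal approximation.

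| CV (assumed) | SE, days | 95% half-width, days | True difference 0: chance the estimate lies within 0.1 day of zero | True difference 0.5 day: chance the 95% CI includes 0 | True difference 1 day: chance the 95% CI includes 0 |
|---|---|---|---|---|---|
| 0.7 | 0.235 | 0.46 | 33% | 43% | 1% |
| 1.0 | 0.335 | 0.66 | 24% | 68% | 15% |
| 1.5 | 0.503 | 0.99 | 16% | 83% | 49% |

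At a true difference of 0 the sign of the denominator is a coin flip, and its 95% CI includes 0 in 95% of trials. The half-day column is the 12 hours that section 4.4 ties to its margin (10% of 5 days).

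**4. Spread of the ratio, costs also equal as hypothesised.** Simulation with both true differences 0, CV 0.7, and cost measured in units of one ventilation day with the same SE as the days (assumption). Ventilation cost is part of the numerator, so saved days should go with lower cost; the correlation is given as its size.

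| Correlation, size | Middle 95% of ICERs (day-costs per day) | ICER negative |
|---|---|---|
| 0 | −12.5 to +12.6 | 50% |
| 0.5 | −11.2 to +10.5 | 67% |
| 0.9 | −6.5 to +4.7 | 86% |

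At 0.9 the negative values split 42.9% cheaper-and-better against 42.8% dearer-and-worse. The sign does not show which arm is favoured.

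**5. Spread of the ratio with a real saving.** Assumed true cost difference −500 euro and cost SD 8,000 euro (neither is in the protocol), so SE of the cost difference = 8,000 × sqrt(2/445) = 536 euro. True effect difference 0. Middle 95% of ICERs, euro per day, rounded:

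| CV | Correlation 0 | Correlation 0.7 in size |
|---|---|---|
| 0.7 | −41,000 to +41,000 | −38,000 to +35,000 |
| 1.0 | −29,000 to +28,000 | −27,000 to +25,000 |
| 1.5 | −19,000 to +19,000 | −18,000 to +16,000 |

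The euro limits move with the assumed inputs. That the interval covers large values of both signs does not; it comes from a denominator centred at zero.

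No such calculation is possible for TISS/NAS, because the protocol gives neither its mean nor its variability. There the point rests on the hypothesis of equality alone.

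**The case against.** The strongest reply is that the economic evaluation does not depend on the ratio. Section 9.4.1 plans cost differences with 95% CIs, 9.4.4 a bootstrap of resource-use differences with scenario and sensitivity analyses, and 9.5 a budget impact analysis. If effects are equal, the natural economic result is the cost comparison, and it is planned. This stands. A reader might infer that the protocol offers nothing but the ratio, or that the whole economic conclusion could reverse through noise in the denominator. The documents support neither; the problem is confined to the ICER.

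A reader might also infer that any interval around the ICER would have wrong coverage. The protocol specifies no interval for the ICER; its bias-corrected bootstrap is stated for differences in resource use. Only if that method were carried over to the ratio would poor coverage follow: about 49% to 62% in simulation at a true difference of 0.1 day. A percentile bootstrap interval in the same setting covers about 90% to 96%, though it is wide and uninformative.

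A third reply is that superiority might be shown, which section 9.1 allows for. A true saving of one day would usually give a usable denominator at a CV of 0.7 to 1.0. That is correct, but it is not the scenario the trial is sized for.

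A fourth is that net benefit and similar displays belong in an analysis plan, which is not at hand. Their absence is indeed no fault here. The point concerns the summary that the protocol does fix, which an analysis plan following it would inherit.

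**Conclusion.** The point holds in a limited form. Sections 7.1.3, 9.4 and 9.4.4 fix the cost-effectiveness result as an ICER, with two different denominators. The hypotheses put both at about zero: directly for TISS/NAS, by inference for ventilation-days. If the trial succeeds as hypothesised, the sign and size of the ICER are mostly noise, and a negative value cannot be read.

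The size for ventilation-days is an SE of 0.23 to 0.50 day around an expected zero, and a denominator whose 95% CI includes 0 in 43% to 83% of trials even at a true 12-hour difference. This rests on the 5-day mean and 445 per arm in section 4.4 and on an assumed CV of 0.7 to 1.5. The euro ranges, roughly ±16,000 to ±41,000 per day, also rest on assumed costs and are illustrations only.

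Severity is minor to moderate. The ICER is an other study parameter; the primary analysis, the safety monitoring and the remaining economic outputs are unaffected.

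**What to change.** In sections 7.1.3, 9.4 and 9.4.4:

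- Name one effect measure for the economic evaluation, so that the three places agree.
- Make the between-arm cost difference with its bootstrap 95% CI the main economic result. Section 9.4.1 already plans the difference and its interval.
- Present cost and effect differences jointly from the same bootstrap samples: the cost-effectiveness plane with the proportion of samples in each quadrant, and net monetary benefit over a stated range of values per unit of effect.
- Report any ICER as secondary, beside that joint display. Do not make its reporting depend on statistical significance.

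The cost is a change of wording and a little more analysis. A range of values per unit of effect has to be stated and defended. No new data are needed.
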